1. OBJECTIVES

1.1 Primary Objectives:

- To determine the response rate to crenolanib, including the rates of complete remission (CR), CR with incomplete blood count recovery (CRi), and partial remission (PR), in relapsed/refractory AML patients with FLT3 activating mutations after first cycle (28-days) and at best response.
- To determine the safety and tolerability of crenolanib in AML patients with FLT3 activating mutations

1.2 Secondary Objectives:

- To determine the duration of response in AML patients with activating FLT3 mutations treated with crenolanib
- To determine the progression free survival and overall survival of AML patients with activating FLT3 mutations treated with crenolanib
- To characterize crenolanib pharmacokinetics in adult patients with AML and relate crenolanib exposure to outcome (e.g., toxicity and/or FLT3 inhibition)
- To analyze phospho-FLT3 and other pharmacodynamic markers from serially collected circulating leukemic blasts and/or marrow blast samples

2. SYNOPSIS

Study Rationale

Protocol: ARO-005

Activating mutations of FLT3 including internal tandem duplication (ITD) mutations within the juxtamembrane domain and single base pair mutations within the tyrosine kinase domain (TKD) of the receptor are the most frequent mutations described in AML, with a prevalence of approximately 30%. Despite the presence of these mutations, there is no approved target specific therapy for AML patients who harbor them.

Crenolanib besylate (CP-868,596-26) is an orally bioavailable, selective tyrosine kinase inhibitor (TKI) of both wild-type FLT3 as well as FLT3 with activating mutations. Crenolanib has a high affinity for mutant FLT3 with K_d values of 0.43nM, 0.18nM, and 0.4nM for FLT3 ITDs and TKD mutations D835Y and D835H, respectively. This high affinity of crenolanib allows it to inhibit aberrant FLT3 signaling at clinically achievable concentrations in AML patients. The activity of crenolanib against wild type FLT3 and FLT3 with activating mutations has been confirmed in both myeloid leukemia cell lines as well as in primary leukemic blasts obtained from patients. Crenolanib was found to be cytotoxic to leukemic blasts from treatment naïve patients with FLT3 activation as well as patients whose leukemia had progressed after chemotherapy or treatment with other FLT3 TKIs.

This pilot Phase II study is designed to evaluate the efficacy and tolerability of crenolanib in two cohorts of AML patients with FLT3 activation mutations (patients whose leukemia has recurred after prior chemotherapy not including a FLT3 TKI and patients whose leukemia has progressed after prior therapy with a FLT3 TKI).

Clinical Protocol Synopsis

Protocol Number: ARO-005

Name of Investigational Product:

Crenolanib besylate (CP-868,596-26)

Title of Study: A Phase II Study of Crenolanib in relapsed/refractory Acute Myeloid Leukemia patients with activating FLT3 mutations.

Number of Planned Patients:

70 patients

Length of Study: 1 year

Objectives:

Primary Objectives

- To determine the response rate to crenolanib, including the rates of complete remission (CR), CR with incomplete blood count recovery (CRi), and partial remission (PR), in relapsed/refractory AML patients with FLT3 activating mutations after first cycle (28-days) and at best response.
- To determine the safety and tolerability of crenolanib in AML patients with FLT3 activating mutations

Secondary Objectives

- To determine the duration of response in AML patients treated with crenolanib
- To determine the progression free survival and overall survival in AML patients with FLT3 activating mutations treated with crenolanib
- To characterize the pharmacokinetics of crenolanib in adult patients and relate drug disposition to outcome or pharmacodynamic markers (i.e. toxicity and/or FLT3 inhibition)
- To analyze phospho-FLT3 and other pharmacodynamic markers from serially collected circulating leukemic blasts and/or marrow blast samples

Study Design:

Protocol: ARO-005

This is a Phase II open label study of crenolanib besylate given three times a day (preferably every eight hours) continuously until one of the criteria for study discontinuation is fulfilled.

The study will enroll 2 different cohorts of patients in parallel.

Cohort A: Will enroll relapsed/refractory AML patients with FLT3 activating mutations who progressed on one or more prior chemotherapy regimens excluding a FLT3 TKI

Cohort B: Will enroll relapsed/refractory AML patients with FLT3 activating mutations whose leukemia has progressed and have history of prior therapy with one or more FLT3 TKIs.

Diagnosis and Main Criteria for Inclusion and Exclusions:

Inclusion Criteria:

- Confirmed primary AML relapsed or refractory after prior therapy, AML secondary to antecedent chemotherapy or radiation therapy, or AML due to prior myelodysplastic syndrome (MDS)/ myeloproliferative neoplasm (MPN) as defined by WHO criteria with presence of either FLT3 ITD and/or other FLT3 activating mutations
- Patients with secondary AML should have failed no more than two (2) prior regimens
- Patients with antecedent MDS/MPN, defined by WHO criteria, without any prior therapy for AML, regardless of the number of therapies for MDS/MPN
- Patients with primary AML should have received no more than two (2) prior cytotoxic containing salvage regimens. Reinduction with the same regimen or stem cell transplant will not be considered a separate salvage regimen. Change of drugs will be considered a salvage regimen. Unlimited FLT3 TKI therapy (even in combination with cytotoxics/hypomethylating agents) is allowed for patients enrolled in cohort B.
- Patients must have tested positive for FLT3-ITD and /or other FLT3 activating mutations within 30 day screening period.
- Males and females age ≥ 18 years
- ECOG PS 0-2
- Adequate liver function, defined as bilirubin ≤1.5x ULN, ALT ≤3.0x ULN, and AST ≤3.0x ULN
- Adequate renal function, defined as serum creatinine $\leq 1.5 \text{x ULN}$
- Recovery from non-hematological toxicities of prior therapy (including HSCT) to no more than grade 1 (except alopecia)
- Subjects should have received no anti-leukemic therapy (except hydroxyurea) prior to the first dose of crenolanib as follows: for 14 days for classical cytotoxic agents and for five times the t_{1/2} (half-life) for FLT3 inhibitors and antineoplastic agents that are neither cytotoxic nor FLT3 inhibitors (e.g. hypomethylating agent or MEK inhibitor). Refer to Appendix XVI for half-life information and drugs considered as FLT3 inhibitors for purposes of this trial.
- Negative pregnancy test for WOCBP.
- Able and willing to provide written informed consent.

Exclusion Criteria:

- Absence of a FLT3 activating mutation
- <5% blasts in blood or marrow at screening
- Concurrent chemotherapy, or targeted anti-cancer agents, other than hydroxyurea.
- Patient with concurrent severe and/or uncontrolled medical conditions that in the opinion of the investigator may impair the participation in the study or the evaluation of safety and/or efficacy.
- HIV infection or active hepatitis B (defined as hepatitis B surface antigen positive) or C (defined as hepatitis C antibody positive)
- Known clinically active central nervous system (CNS) leukemia
- Patients less than 30 days post HSCT.
- Subjects who have clinically significant graft versus host disease requiring treatment and /or have >grade 2 persistent non hematological toxicity related to transplant
- Prior crenolanib treatment for a non-leukemic indication
- Major surgical procedures within 14 days of Day 1 administration of crenolanib.
- Unwillingness or inability to comply with protocol.

Test Product, Dosage and Mode of Administration:

Crenolanib besylate, 100 mg TID (preferably every eight hours), taken orally at least 30 minutes pre or post meal. Patients will complete a daily diary to record the date, time and amount (number of tablets) of crenolanib taken and eating schedule.

Concurrent hydroxyurea (maximum 5g total daily dose x 14 days) is permitted during the first 28 days of study therapy.

Planned Duration of Treatment:

The anticipated duration of patient involvement is a minimum of 28 days with a maximum of 365 days but assessed individually for each patient. Patients will take crenolanib besylate daily until their disease has progressed, the patient has died, or the patient discontinues for adverse events, investigator's judgment, or other reasons

Patients who have discontinued study drug will continue to be followed for 30-days post last dose.

Reference Therapy, Dose and Mode of Administration:

No comparators will be used.

Criteria for Evaluation:

International Working Group for AML (Cheson, et. al., JCO, 2003)

Statistical Methods:

Protocol: ARO-005

The primary end-point is overall response rate. The overall response rates in the two cohorts will be evaluated along with its 95% confidence interval at the end of cycle 1 (28-days) and at best response. Analysis of secondary endpoints will be predominantly descriptive statistics and will be interpreted as being exploratory and hypothesis generating. Duration of response, Progression Free Survival (PFS) and Overall Survival (OS) will be estimated using the method of Kaplan-Meier. In addition, if at any time unacceptable toxicity is encountered in greater than 30% of patients, accrual will be stopped and lower doses of crenolanib may be investigated.

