10.2 Dose Reductions for Non-Hematologic Toxicities

Dose reductions for non-hematologic toxicities due to crenolanib, will be done according to the schema outlined in Table 10.1.

• Reductions below 60mg TID are not planned; dose reductions beyond those mentioned in this table or different than those specified, should be discussed with the sponsor and documentation justifying the specified dose recorded. If an appropriate dose is not determined, then it will lead to patients' withdrawal from the study drug, in which the patient will stop taking crenolanib, but will still be followed for outcomes.

Dose level	Crenolanib dosing
0	100 mg TID
-1	80 mg TID
-2	60 mg TID

Table 10.2. Crenolanib dose reduction guidelines

Toxicity	Dose Modification
(NCI Criteria)	
Grade 1 or 2	No dose modification
Clinically significant	Hold drug until toxicity resolves to grade 1 or less. Restart drug
persistent grade 2	at same dose level (Table 10.2).
despite optimal therapy	

Hold drug until toxicity resolves to grade 1 or less. Restart drug
at next lower dose level (Table 10.2).

Table 10.3. Crenolanib dose reduction guidelines for All Toxicities (except GI (nausea, vomiting and diarrhea)) related to study drug.

Starting dose (dose level 0) for all patients will be 100 mg TID. A maximum of two (2) dose reductions are allowed in a single patient for toxicity management.

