- 2) Renal failure related to tumor lysis syndrome or antibiotic/ antifungal therapy
- 3) Rash related to antibiotic use
- 4) Hospitalization for the management of any of the above expected events

Reporting Hematology and Blood Chemistry Results:

- Hematology and blood chemistry results for every scheduled visit or for the most contiguous to the scheduled visit should be reported on case report form. Data captured in addition to the protocol specified scheduled visit is to be captured, only if any abnormal hematological or chemical values resulted in dose modification or dose delay.
- Transfusion information is to be captured throughout the study.

Adverse Event Reporting in 30-day Follow-up Period:

- Adverse events will be captured from the time the patient signs consent until 30 days after the last dose of study drug.
- If patients goes on to another clinical study or standard therapy, if possible, adverse events should continue to be captured for 30 days, including name of new therapy.
- Patients who do not have progressive disease but stop crenolanib for toxicity, should be followed until resolution of toxicity.

 Patients who have progressive disease and do not receive further therapy do not need to be followed, unless there is toxicity related to study drug which is unresolved at the time patient is taken off study

15.2 Serious Adverse Event (SAE) Reporting:

A serious adverse event is – any adverse drug experience occurring at any dose that results in any of the following outcomes:

Death

Protocol: ARO-005

- A life-threatening adverse drug experience any adverse experience that places the patient, in the view of the initial reporter, at immediate risk of death from the adverse experience as it occurred. It does not include an adverse experience that, had it occurred in a more severe form, might have caused death.
- Inpatient hospitalization or prolongation of existing hospitalization
- A persistent or significant disability/incapacity a substantial disruption of a person's ability to conduct normal life functions.
- A pregnancy or congenital anomaly/birth defect.

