16.3 Statistical and Analytical Plans

The primary end-point is overall response rate. The overall response rates in the two cohorts will be evaluated along with its 95% confidence interval. Analysis of secondary endpoints will be predominantly descriptive statistics and will be interpreted as being exploratory and hypothesis generating. Progression free survival (PFS) and overall survival (OS) will be estimated using the method of Kaplan-Meier. Cox regression models will be used to determine the relationship with the time-to-events (e.g. PFS and OS) and the potential prognostic factors. Exploratory logistic regression will be used to identify the prognostic factors that are significantly correlated with the response rate.

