Appendix V. Study Schedule

	screening	Therapy							End	Follow-		
Cycle No	Jercennig		1					2	2		of	up visit
Cycle No.								2	3	n	Study	
Duration			28d			2	.8d	28d	28d	visit		
Relative day within cycle	(-)14	1	2	8	15	22	1	15	1	1		
Informed Consent	Х											
Inclusion/Exclusion	Х											
Demography	Х											
Relevant medical history, current medical conditions including AML- specific history	X	Х										
Evaluation of FLT3- D835, FLT3-ITD, and other mutational status	Х											
Height	Х											
Prior/Concomitant medications, significant non- drug therapies	Х	Х	Х	Х	Х	Х	Х	Х	Х	Х	Х	Х
Physical examination ¹	Х	Х					Х		Х	Х	Х	Х
Vitals, ECOG Performance Status, Weight	Х	Х		Х	Х	Х	Х	Х	Х	Х	Х	Х
AEs and SAEs	Х	Х	Х	Х	Х	Х	Х	Х	Х	Х	Х	Х
Laboratory tests												
Hematology ²	Х	X X		XX	Х	Х	Х	Х	Х	Х	Х	Х
Serum Chemistries ²	Х	XX		XX	Х	Χ	Х	Х	Х	Х	Х	Х
HIV, HepB/C	Х											
Urine or serum Pregnancy test	Х										Х	
Peripheral blood for PK analysis ³		Х	Х		Х		Х		Х			
Peripheral blood for correlative analysis ³		Х	Х		Х							
Disease assessment												
Bone marrow aspirations (x2) ⁴	X	X	1				Х		Х	Х		

¹Physical examination = .Day 1 +/- 4 days

 $^{^2}$ CBC includes platelet count, differential (differential may be omitted if WBC is <0.5 x10 9 /L), Chemistry panel including AST, ALT, and total bilirubin to be drawn twice weekly (at least 24 hours apart) for the first two weeks of

cycle 1, once weekly (± 3 days) for the second two weeks of cycle 1, bi-weekly (± 4 days) for the second cycle and once a month thereof from cycle 3 until cycle 12 (\pm 14 days).

Labs obtained with the local physician can be used for monitoring; PI must review and sign source documents within 24 hours of performance of lab at local physician's office unless performed on a Friday in which case review on the following Monday is acceptable. It is encouraged that labs be performed on Monday thru Thursday. At the time of any dose escalation, labs should be drawn twice per week for at least one week.

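### Overall survival is a secondary endpoint, but no general survival follow-up is written beyond 30 days after the last dose, so the Kaplan-Meier curve would be informatively censored

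*Combined protocol and SAP*

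**What the plan says.** Section 1.2 lists the objective: "To determine the progression free survival and overall survival of AML patients with activating FLT3 mutations treated with crenolanib". Section 16.3 gives the analysis: "Progression free survival (PFS) and overall survival (OS) will be estimated using the method of Kaplan-Meier". It adds: "Cox regression models will be used to determine the relationship with the time-to-events (e.g. PFS and OS) and the potential prognostic factors".

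Follow-up after stopping is described in several places:

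- **Synopsis, Planned Duration of Treatment:** this sets the expected time in the study: "The anticipated duration of patient involvement is a minimum of 28 days with a maximum of 365 days but assessed individually for each patient". Then, for anyone off drug: "Patients who have discontinued study drug will continue to be followed for 30-days post last dose". This is the only rule that applies to all patients.
- **Section 10.2:** where no suitable reduced dose can be settled on, "the patient will stop taking crenolanib, but will still be followed for outcomes". It covers that route alone and gives no schedule or duration.
- **Section 15.1, 30-day follow-up period:** "Patients who have progressive disease and do not receive further therapy do not need to be followed, unless there is toxicity related to study drug" that remains unresolved. Patients who stop for toxicity without progression are followed until it resolves. Section 7 also asks for reassessment to resolution after a toxicity stop.
- **Section 15.2:** after 30 days, only treatment-related serious events are reported.
- **Appendix V:** one end-of-study visit and one follow-up visit with no stated timing. There is no survival-status row and no repeated contact.
- **Section 16.4:** the study is complete after an unspecified data cut-off.

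Section 16 defines neither the OS and PFS events nor how either endpoint is censored.

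**The concern.** Kaplan-Meier and Cox estimates need censoring that says nothing about later risk. Here the censoring clock starts when drug is stopped, and patients stop for progression, adverse events or the investigator's judgment. Those who leave the risk set 30 days later are therefore a selected group, and the curve carries on from those still on drug or only just off it.

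If the death hazard rises after stopping, the curve is too high. If it does not, the bias vanishes or reverses. The trial's own data could not show which case applied, because deaths after the 30 days need not be recorded. The OS curve and the OS Cox models could then not be read as overall survival.

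PFS is less exposed. A patient who stops at progression already has the event. PFS and duration of response are affected only through stops without progression: toxicity, patient request, or the planned transplant in Section 7.

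**Working it through.** The plan states no OS figure (no median, event count or follow-up time), so there is nothing of its own to reproduce. The calculation below is illustrative.

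**Inputs from the documents.** OS is censored 30 days after last dose (synopsis), taken as 1 month. Treatment is capped at 12 cycles of 28 days (Section 9.4): 12 × 28 = 336 days, or 11.0 months.

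**Assumed inputs.** Time on drug is exponential with median m₁ (2 or 3 months), hazard λ = ln 2/m₁. A share d of stops before the cap are deaths (15%, 30% or 50%). The other patients survive a further exponential time with median m₂ (3 or 6 months), hazard μ = ln 2/m₂.

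**True survival** before the cap:

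S(t) = e^(−λt) + [(1−d)λ/(λ−μ)] × [e^(−μt) − e^(−λt)]; if λ = μ, S(t) = e^(−λt)[1 + (1−d)λt].

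**What Kaplan-Meier estimates.** The risk set holds patients on drug plus those who stopped alive within the last month and are still alive. From month 1 to the cap, the ratio of the second group to the first is

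r = (1−d)λ × [1 − e^(−(μ−λ))]/(μ−λ) (the fraction is 1 if λ = μ),

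and the estimated hazard is h = (dλ + μr)/(1 + r).

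**Worked case: m₁ = 2, m₂ = 3, d = 15%.** λ = 0.3466 and μ = 0.2310.

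- True 6-month OS: 0.125 + (0.85 × 0.3466/0.1155) × (0.25 − 0.125) = 0.125 + 2.55 × 0.125 = 44.4%.
- r = 0.85 × 0.3466 × 1.060 = 0.312.
- h = (0.0520 + 0.0722)/1.312 = 0.0946 per month. In the first month h climbs from 0.0520 to 0.0946, with average 0.0748.
- Kaplan-Meier 6-month OS: exp(−(0.0748 + 5 × 0.0946)) = exp(−0.548) = 57.8%.
- Kaplan-Meier median: 1 + (0.6931 − 0.0748)/0.0946 = 7.5 months. Solving S(t) = 0.5 gives a true median of 5.3 months.

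| Median on drug / after stopping (months) | Stops by death | Median OS, true vs Kaplan-Meier (months) | 6-month OS, true vs Kaplan-Meier |
|---|---|---|---|
| 2 / 3 | 15% | 5.3 vs 7.5 | 44% vs 58% |
| 2 / 3 | 30% | 4.6 vs 5.4 | 39% vs 46% |
| 2 / 3 | 50% | 3.7 vs 3.8 | 31% vs 34% |
| 3 / 3 | 15% | 6.6 vs 10.6 | 54% vs 68% |
| 3 / 3 | 30% | 5.9 vs 7.7 | 49% vs 58% |
| 3 / 6 | 50% | 6.0 vs 6.0 | 50% vs 50% |
| 2 / 6 | 30% | 6.3 vs 6.5 | 52% vs 53% |
| 2 / 6 | 50% | 4.5 vs 4.2 | 41% vs 37% |

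Simulation with 400,000 patients per row agrees to within about 0.1 month and 1 point.

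**Where the sign changes.** The bias is zero when the two death hazards are equal, dλ = μ, that is d = m₁/m₂: 67% at 2/3, 50% at 3/6, 33% at 2/6.

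**Deaths recorded.** With p = e^(−11.0λ) reaching the cap, the share is d(1−p) + [1 − d(1−p)] × (1 − e^(−μ)). At 2/3 months this is 32%, 44% and 59% for d = 15%, 30% and 50%.

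**A second model.** Here both curves run to day 365. The median time to stopping is 45–90 days, and median survival is 180–365 days at the on-drug death rate and 60–120 days off drug. The 30-day rule raises 6-month OS by about 7–16 points and median OS by 17–71 days, and observed deaths fall from 79–97% to 25–48%. With a 365-day median both on and off drug, the bias is about zero, but observed deaths still fall from 50% to 16–24%.

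**PFS.** Time on drug has a median of 2 months. If every stop is progression or death, true and estimated 6-month PFS are both 12.5%. If 30% stop without progression, the estimate is about 5 points too low when the later event hazard is 0.4 times the on-drug one (about 31% true vs 25%). It is about 3 points too high when that hazard is doubled (about 18% vs 21%).

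**The case against.** The strongest reply is that the plan is under-specified and does not set out to censor OS at 30 days. The sentence sits in the synopsis under treatment duration, its 30 days match the adverse-event window, and nothing forbids later survival contact. Section 10.2 shows that outcome follow-up after stopping was in mind. Toxicity follow-up can run past 30 days, so vital status would be known for longer in that subgroup than the model assumes. This stands in part: sites may collect survival anyway. But no passage requires it, uneven voluntary collection is itself a source of bias, and none of these passages covers patients who stop at progression. Section 15.1 releases such patients if they have no further therapy and no unresolved drug toxicity.

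The second reply is that the size is wholly assumed, and that nothing in the documents favours 15% of stops by death over 50%, where the bias nearly disappears. That is correct, and the figures should be read as a range with either sign.

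The third is about weight. OS is secondary and exploratory in a single-arm study, and no decision rule uses it. Sampling error on 6-month OS is also large: 1.96 × √(0.44 × 0.56/30) = 18 points for 30 patients, and 1.96 × √(0.31 × 0.69/40) = 14 points for 40. This limits the severity. The bias, however, does not shrink with more patients, and the confidence interval would not show it.

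**Conclusion.** The concern holds. The one general rule after stopping is 30 days, the schedule collects no survival status and no censoring rule is written. Following the plan as it stands would censor OS at a time tied to prognosis. In the cases tabulated, the error in median OS runs from 0.3 months too low to 4.0 months too high, and in 6-month OS from 3 points too low (before rounding) to 14 points too high. These sizes depend on assumed exponential hazards, on 30 days being applied to everyone who leaves drug alive, and on no outside survival collection. The direction depends on whether the death hazard is higher after stopping than on drug. PFS bias is smaller and arises only from stops without progression. The primary response-rate analysis and the two-stage decisions are untouched. This should be fixed, but it does not undermine the trial's main conclusion.

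**What to change.** Add one rule: every treated patient, whatever the reason for stopping, is followed for vital status by telephone or chart check about every 2–3 months until death, withdrawal of consent or the data cut-off in Section 16.4. For patients who stop without progression, record relapse or progression dates from routine care. Define the OS, PFS and duration-of-response events and their censoring, with OS censored at the date last known alive. Add a survival row to Appendix V and make it agree with the synopsis, Section 10.2 and Section 15.1.

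The cost is a protocol amendment, brief status contacts for about 70 patients, some chart review for relapse dates, and possibly a consent update, since Appendix I treats the consent form as part of the protocol and the synopsis caps anticipated involvement at 365 days. No visits, procedures or assessors are added. If this is declined, drop OS or label the curve as survival to 30 days after last dose.
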